Vital signs	X	Daily										X	X	X		Documentation of hospital-based exam is acceptable. Includes: body temperature, pulse rate, BP, SpO ₂ , respiratory rate, FiO ₂ if known, and method of delivery, if applicable. Record while participant is at rest.

Procedures	Screening	Evaluation Period										ETV	Post-Evaluation Follow-Up			Comments
Study Day	Max 7-day window	1	2-7	8	15	22	29	36	43	50	57		85	141	169	
Visit window (\pm number of days)	--	--	--	2	2	2	2	2	2	2	2		7	7	7	
Hospitalization events		Daily										X	X	X		Record if the following events occur: 
Emergency room visitshospitalizedICU admittance,Extended care facility admittance,and discharge for any of the above
Clinical status and concomitant procedures of special interest in hospitalized participants		Daily										X	X	X		Documentation from hospital records is acceptable. Includes: consciousness status (ACVPU), limitation on activities due to COVID-19, and requirements for 
Ongoing hospital medical careSupplemental oxygennon-invasive ventilation or a high flow oxygen devicemechanical ventilationextracorporeal membrane oxygenation, oradditional organ support (e.g. pressors, renal replacement)
Clinical symptoms and interventions of interest		Daily										X	X			See Table 1 for clinical symptoms and interventions of interest.

Procedures	Screening	Evaluation Period										ETV	Post-Evaluation Follow-Up			Comments
Study Day	Max 7-day window	1	2-7	8	15	22	29	36	43	50	57		85	141	169	
Visit window (\pm number of days)	--	--	--	2	2	2	2	2	2	2	2		7	7	7	
Symptoms Questionnaire	X	Daily										X	X		See Section 8.1.2.	
SARS-CoV-2 POC Test (Nasal Swab)	X														Applies to participants in Part 2 only. Result must be determined prior to collecting swabs for PCR test.	
SARS-CoV-2 Serology		X				X			X	X	X	X	X	X	Day 1: pre-dose. assessed at a central laboratory	
SARS-CoV-2 nasopharyngeal swab (for PCR test) taken from both nostrils		X													Day 1: pre-dose. assessed at a central laboratory	
SARS-CoV-2 nasal swab (for PCR test) taken from both nostrils		X		X	X	X	X	X	X	X	X	X	X		Day 1: pre-dose. assessed at a central laboratory No samples needed if participant is hospitalized.*	

Procedures	Screening	Evaluation Period										ETV	Post-Evaluation Follow-Up			Comments
Study Day	Max 7-day window	1	2-7	8	15	22	29	36	43	50	57		85	141	169	
Visit window (\pm number of days)	--	--	--	2	2	2	2	2	2	2	2		7	7	7	

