The maximum total duration of study participation for each participant of the treatment group is 12 weeks. See the SOA for the treatment group in Section 1.3.2.

This table describes the visit types for the prevention population for this study.

Study Day	Activity	Visit Type
0,1	Follow SoA	Onsite
8, 15, 22, 29, 36, 43, 50, 57	Follow SoA Vital signs*	Onsite or Home (Virtual [record collection] if hospitalized)

Daily 2 - 57	Vital signs and symptoms questionnaire daily* Vital signs, clinical status, and concomitant procedures for hospitalized participants.	Onsite or Home (Virtual [record collection] if hospitalized)
ETV and follow-up (85, 141, 169)	Follow SoA	Onsite or Home

*Collected via direct data capture for onsite or home visits only.

This table describes the visit types for the treatment population for this study.

Study Day	Activity	Visit Type
0, 1	Follow SoA	Onsite
8, 29	Follow SoA Vital signs*	Onsite or Home (Virtual [record collection] if hospitalized)
Daily 2-29	Vital signs, clinical status, and concomitant procedures for hospitalized participants.	Virtual (record collection) if hospitalized
ETV and follow-up (85)	Follow SoA	Onsite or Home

*Collected via direct data capture for onsite or home visits only.

Hospitalization

If a participant is hospitalized, efforts will be made to retrieve hospital records and report procedures and assessments according to the SoA, as feasible.

Definitions for COVID-19 Severity

This table gives the definitions for COVID-19 severity of illness for those participants who are SARS-CoV-2 positive as determined by standard RT-PCR assay or equivalent test.

Table 1 Definitions for COVID-19 Severity

Severity	Description
Mild	Mild symptoms that could include: 
 fever, cough, sore throat, malaise, headache, muscle pain, gastrointestinal symptoms, without shortness of breath or dyspnea AND No clinical signs indicative of Moderate, Severe, or Critical Severity
Moderate	Symptoms of moderate illness with COVID-19, which could include any symptom of mild illness or shortness of breath with exertion AND Clinical signs suggestive of moderate illness with COVID-19, such as: 
 respiratory rate \geq 20 breaths per minute,

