### ***6.3.3. Non-Responder Imputation (NRI)***

For analysis of other categorical efficacy, missing data will be imputed using a NRI method. Patients will be considered nonresponders for the NRI analysis if they do not meet the categorical efficacy criteria or have missing clinical efficacy data at a time point of interest.

In addition, patients who were not adequately assessed to determine if they meet the clinical requirements for response at the time point of interest are also considered to have failed treatment.

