#### 6.16.1.3. SARS-CoV-2 Clearance

For qualitative determination of viral clearance, the lab determination of “positive”/“negative” will be used. SARS-CoV-2 clearance (yes/no) is defined as a single negative RT-PCR test for the SARS-CoV-2 virus. The date of viral clearance is defined as the date of the first occurrence of a negative test.

The proportion of patients that achieve SARS-CoV-2 clearance within 1, 2, or 3 weeks of becoming SARS-CoV-2 positive will be summarized by treatment group in frequency tables and listed for the Prevention populations and the Part 1 Treatment population. Similar summaries will be made for the proportion of patients in the Part 2 Treatment and Part 3 treatment populations that achieve SARS-CoV-2 clearance within 8 and 29 days of becoming SARS-CoV-2 positive.

In addition, the number of patients that achieve SARS-CoV-2 clearance within 1, 2, or 3 weeks (or, for the Part 2 Treatment and Part 3 treatment populations, within 8 and 29 days) of becoming SARS-CoV-2 positive will be analyzed using logistic regression to compare treatment groups, if there are sufficient data available. Missing data will be imputed using the NRI method as described in Section 6.3.3. This comparison will be made on the Prevention and Treatment populations.

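### Non-responder imputation counts Prevention participants as not cleared when their 1-, 2- or 3-week clearance window runs past the last weekly swab at Day 57

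*SAP*

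**What the plan says.** - **Endpoint.** SAP 6.16.1.3 summarises, for the Prevention populations and the Part 1 Treatment population, "The proportion of patients that achieve SARS-CoV-2 clearance within 1, 2, or 3 weeks of becoming SARS-CoV-2 positive". Clearance "is defined as a single negative RT-PCR test for the SARS-CoV-2 virus", so at least one swab after the first positive is needed to show it.
- **Missing data.** After the logistic regression the section adds: "Missing data will be imputed using the NRI method as described in Section 6.3.3. This comparison will be made on the Prevention and Treatment populations". SAP 6.3.3 defines the rule: "Patients will be considered nonresponders for the NRI analysis if they do not meet the categorical efficacy criteria or have missing clinical efficacy data". It also counts as treatment failures "patients who were not adequately assessed to determine if they meet the clinical requirements for response at the time point of interest".
- **Swab schedule.** The Protocol 1.3.1 row for "SARS-CoV-2 nasal swab (for PCR test) taken from both nostrils" marks the weekly evaluation visits, the early termination visit and Day 85. The Prevention evaluation visits in Protocol 4.1.2 are Days "8, 15, 22, 29, 36, 43, 50, 57". The weekly visits have a window of ±2 days and Day 85 of ±7 days.
- **Time frame.** Protocol Section 3 sets 8 weeks from randomization for the Part 1 exploratory Prevention endpoints.
- **Companion analysis.** SAP 6.16.1.4 analyses time to the same clearance event. It censors anyone not yet cleared at their last evaluation-period visit.

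**The concern.** The clearance window starts at the first positive swab, which can be any weekly visit up to Day 57, but weekly swabbing stops at Day 57. For late first positives, part or all of the window cannot be observed. SAP 6.16.1.3 does not exclude, censor or weight these participants. The weighting in SAP 6.3.1 and 6.3.2 covers only primary and key secondary endpoints. NRI therefore turns a limit of the visit schedule into a treatment failure, while the next section censors the same people.

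At stake is the reading of a virological endpoint in breakthrough infections. Both arms' proportions are too low. If infections come later in one arm, that arm appears to clear virus less often even when true clearance is the same. The two clearance analyses could then disagree because of the schedule alone.

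**Working it through.** The plan gives no figure for this endpoint, so there is none to reproduce. The check counts planned swabs and then applies the NRI rule.

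**Step 1. Planned swabs in each window.** Nominal days, using the simple date difference:

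| First positive | 1 week | 2 weeks | 3 weeks |
|---|---|---|---|
| Days 8 to 36 | 1 | 2 | 3 |
| Day 43 | 1 | 2 | 2 |
| Day 50 | 1 | 1 | 1 |
| Day 57 | 0 | 0 | 0 |

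The Day 85 swab can be taken on Day 78 at the earliest, which is 78 − 57 = 21 days after a Day 57 positive. It could fill the 3-week window only in that corner, and only if a post-evaluation swab may count.

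The Part 1 Treatment population is not affected by the Day 57 limit. Its members are positive at Day 1, and Days 8, 15 and 22 cover the three windows.

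**Step 2. Share with an incomplete window.** If first positives are spread evenly over the eight visits (assumed), the shares are 1/8 = 12.5%, 2/8 = 25% and 3/8 = 37.5% at 1, 2 and 3 weeks. Only the Day 57 group (12.5%) fails with certainty.

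**Step 3. Effect on the reported 3-week proportion.** Let h be the chance of a first negative at each weekly swab, equal in both arms, and k the number of swabs in the window. The reported proportion is the sum over visits of (share first positive at that visit) × [1 − (1 − h)^k].

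Take h = 0.35 (assumed):
- k = 3: 1 − 0.65³ = 0.725 (the true 3-week value)
- k = 2: 1 − 0.65² = 0.5775
- k = 1: 0.35
- k = 0: 0

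Assumed timing: 67% of infections at the first four swabs in one arm and 45% in the other, with the rest spread evenly over Days 36, 43, 50 and 57. Each late visit then holds 0.33/4 = 0.0825 or 0.55/4 = 0.1375.

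- Earlier arm: (0.67 + 0.0825) × 0.7254 + 0.0825 × (0.5775 + 0.35) = 0.546 + 0.077 = 0.622
- Later arm: (0.45 + 0.1375) × 0.7254 + 0.1375 × (0.5775 + 0.35) = 0.426 + 0.128 = 0.554

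The false difference is 0.622 − 0.554 = 0.068, about 7 points, with no true difference.

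**Step 4. Sensitivity to h, same timing.**
- h = 0.20 (0.488, 0.36, 0.20): 0.413 against 0.364, about 5 points.
- h = 0.50 (0.875, 0.75, 0.50): 0.762 against 0.686, about 8 points.

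A more extreme assumed timing puts 3%, 4% and 6% of one arm's first positives at Days 57, 50 and 43, against 17%, 17% and 16% in the other. It gives 12 to 18 points over the same range of h.

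**Step 5. Day count.** SAP 6.1.3 and 6.16.1.4 add 1 to date differences. If that convention is used here, the next weekly swab falls on day 8, and nobody on the nominal schedule can clear within 1 week. Separately, the ±2-day windows put consecutive swabs anywhere from 3 to 11 days apart. The 1-week window can therefore be missed at any point in follow-up.

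**The case against.** - **The remedy is already next door.** SAP 6.16.1.4 treats the same event as time-to-event with censoring, and SAP 6.1.4 provides for Kaplan-Meier methods. This stands as mitigation: a sound clearance analysis exists. It does not repair the three proportions, which are still tabulated and tested.
- **Late first positives are not all lost.** A reader might infer that everyone first positive from Day 43 on has no swab. The schedule does not support that. Day 43 and Day 50 first positives have at least one swab in every window, and one negative result suffices. They are under-observed; only Day 57 first positives are near-certain failures.
- **The share with an incomplete window is not the bias.** On the timing in Step 3, 3 × 0.0825 = 25% and 3 × 0.1375 = 41% lack a full 3-week window, which might suggest a 16-point gap. The false gap on that timing is about 7 points, because a shortened window misleads only when the first negative would have come on an unscheduled swab.
- **The arm imbalance is assumed.** A reader might infer that the active arm must look worse. No passage says its infections come later. Protocol 4.3 projects antibody coverage in 90% of participants for 8 weeks at the Part 1 dose. Enrolment within 7 days of an index case suggests early infections in both arms.
- **The early lock is temporary.** A reader might add everyone infected shortly before the Primary Database Lock. SAP 6.1.5 re-evaluates those analyses at the End of Evaluation Database Lock, which removes that truncation. It does not remove the Day 43 to 57 truncation.
- **The stakes are low.** The endpoint is exploratory, and the logistic comparison is run only if data suffice. Because it conditions on infection after randomization, it is not a clean randomized contrast under any handling. All of this stands.

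**Conclusion.** The concern holds as a limited analysis flaw. As written, SAP 6.16.1.3 with 6.3.3 counts Day 57 first positives as failures by construction, apart from the possible early Day 85 swab. It also understates 2- and 3-week clearance for Day 50 first positives and 3-week clearance for Day 43 first positives. The downward bias follows from the documents.

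Its size does not, nor does any difference between arms. The illustration of 0.62 against 0.55, with a true 0.725, rests on assumed infection timing and an assumed common clearance rate per swab. On that timing the false difference is about 5 to 8 points as the rate runs from 20% to 50%, and its direction depends on which arm is infected later. No primary or key secondary result is affected.

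**What to change.** In SAP 6.16.1.3, for the Prevention populations:

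1. Estimate and compare the 1-, 2- and 3-week clearance proportions from Kaplan-Meier curves by arm. Censor participants who have not cleared at their last swab, consistent with SAP 6.16.1.4.
2. Define the windows by scheduled visit: the next one, two or three weekly visits after the first positive. The ±2-day windows and the +1 day count then cannot exclude the next weekly swab.
3. Keep NRI only for swabs that were scheduled before the data cut-off and missed. These count as not cleared at that visit. State how swabs waived during hospitalization are classed, since the Protocol 1.3.1 schedule does not require them.
4. As a sensitivity analysis, limit each denominator to participants with a full scheduled window: first positive by the Day 50, Day 43 or Day 36 visit for 1, 2 or 3 weeks.

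**Cost.** A few sentences in the SAP and no new data. The Kaplan-Meier comparison gives up the facility, role and sex adjustment of the logistic model. It also assumes that late infections clear at the same rate as early ones, which should be stated. The restricted denominator is noticeably smaller at 3 weeks: 62.5% of infected participants remain if first positives are evenly spread, and 75% and 59% in the two arms on the timing in Step 3. That is why it suits a sensitivity analysis better than the main one.

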
 Compare the incidence of SARS-CoV-2 infection Compare the frequency of hospitalization or death due to COVID-19 Characterize clinical status for participants. Compare the mortality due to COVID-19 	
 Cumulative incidence of SARS-CoV-2 infection defined as the detection of SARS-CoV-2 by RT-PCR Proportion of participants who are hospitalized or have died due to COVID-19 Proportion (percentage) of participants who experience these events: 
 COVID-19 related hospitalization (defined as ≥ 24 hours of acute care), COVID-19 related emergency room visit, or death Proportion of participants who die due to COVID-19 (according to the investigator)
Exploratory	
[time frame for endpoint evaluation: 8 weeks from randomization]	

 Compare time to improvement to mild severity symptoms in participants who develop moderate or worse severity^a COVID-19 Characterize COVID-19 illness and severity according to NIAID ordinal scale(s) Characterize SARS-CoV-2 viral endpoints in those participants that become RT-PCR positive Characterize emergence of viral resistance to LY3819253 Compare the duration of hospitalization due to COVID-19 	
 Time to improvement to mild severity^a Worst score on NIAID ordinal scale(s) Proportion of participants that achieve SARS-CoV-2 clearance within 1, 2, or 3 weeks of positive RT-PCR Time to SARS-CoV-2 clearance Comparison from the first positive sample to at least the last positive sample Cumulative days of hospitalization in those who are hospitalized due to COVID-19

Abbreviations: COVID-19 = coronavirus disease – 2019; NIAID = National Institute of Allergy and Infectious Diseases; RT-PCR = reverse transcription – polymerase chain reaction; SARS-CoV-2 = severe acute respiratory syndrome coronavirus 2.

^a As defined in [Table 1](#).

Treatment Population Exploratory Objectives and Endpoints Participants positive at baseline for SARS-CoV-2 RT-PCR and negative at baseline for serology Comparison Groups: Placebo vs LY3819253 4200 mg [time frame for endpoint evaluation: 8 weeks from randomization]	
Objectives	Endpoints

 Compare the frequency of hospitalization or death due to COVID-19 	
 Proportion of participants who are hospitalized or have died due to COVID-19

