### **6.1.3. Study Time Intervals**

To calculate the length of any time interval or time period in this study, the following formula will be used:

$$\text{Length of interval (days)} = \text{End Date} - \text{Interval Start Date} + 1$$

To convert any time length from days to weeks, the following formula will be used:

$$\text{Length of interval (weeks)} = \text{Length of interval (days)}/7$$

Only for the purpose of calculating the length of study period time intervals, the words “prior to” in [Table PYAD.6.2](#) should be understood to mean “the day before” while the words “after” should be understood to mean “the day after.” For the purpose of determining whether a date/time lies within an interval, these words are intended to convey whether the start or end of the period is inclusive of the specified date.

For the purposes of the endpoints assessing the incidence of SARS-CoV-2 infection, the words “by Day 29” should be understood to mean “at any time prior to and including the Day 29 visit, provided the visit occurs within the specified visit window.” The words “by Day 57” should be understood to have a similar meaning. For all other endpoints, similar definitions will apply, but results from visits outside of the specified visit window may be used.

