#### 6.16.1.4. Time to SARS-CoV-2 Clearance

See Section 6.16.1.3 for more details on the definition of viral clearance and date of viral clearance.

Time to SARS-CoV-2 clearance is defined (in days) as:

*(Date of first negative SARS-CoV-2 RT-PCR test – Date of first positive SARS-CoV-2 RT-PCR test + 1)*

Only patients who have at baseline or later develop SARS-CoV-2 infection will be included in the analysis. If a patient has not experienced SARS-CoV-2 clearance by completion or early discontinuation of the evaluation period, the patient will be censored at the date of their last visit during the evaluation period.

Time to SARS-CoV-2 clearance will be evaluated during the study evaluation period only and will be summarized by treatment group, and listed for the Prevention and Treatment populations. Cox proportional hazard methodology will be used.

Time to SARS-CoV-2 clearance will be presented graphically.

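### Under the SAP's own interval rule, a negative swab taken exactly one, two or three weeks after the first positive falls just outside the 1-, 2- and 3-week clearance windows

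*SAP*

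**What the plan says.** The endpoint comes from Protocol Section 3, which lists for the Part 1 Prevention population: "Proportion of participants that achieve SARS-CoV-2 clearance within 1, 2, or 3 weeks of positive RT-PCR". The same section gives a matching endpoint, counted from baseline, for the Part 1 Treatment population. SAP 6.16.1.3 carries these into the analysis as "The proportion of patients that achieve SARS-CoV-2 clearance within 1, 2, or 3 weeks of becoming SARS-CoV-2 positive", and adds: "The date of viral clearance is defined as the date of the first occurrence of a negative test". It gives no counting rule or visit mapping for these windows.

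The general rule is in SAP 6.1.3. It opens "To calculate the length of any time interval or time period in this study, the following formula will be used" and sets the length in days to end date minus start date plus 1. It continues "To convert any time length from days to weeks, the following formula will be used", with weeks equal to days divided by 7. SAP 6.16.1.4 uses the same count for time to clearance: "Date of first negative SARS-CoV-2 RT-PCR test – Date of first positive SARS-CoV-2 RT-PCR test + 1".

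For Part 2 Treatment and Part 3, SAP 6.16.1.3 states the windows in days instead, as patients who "achieve SARS-CoV-2 clearance within 8 and 29 days of becoming SARS-CoV-2 positive".

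The schedule in Protocol 1.3.1 covers Part 1 and the Part 2 Prevention Cohort. It places PCR swabs on Day 1 and then weekly from Day 8 to Day 57, with a visit window of plus or minus 2 days from Day 8 onward.

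**The concern.** With weekly swabs, a one-week clearance window has one natural purpose: to capture the swab taken one week after the positive. The plus-1 count makes that swab 8 days old, and 8 days is more than one week. The same happens at two and three weeks. The swab that each window appears designed around is the one it excludes when the participant attends on the planned day.

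What is at stake is the meaning and reproducibility of the reported rates. With on-schedule visits, the 2-week rate describes what was known at one week, and the 3-week rate what was known at two. A first negative at the three-week swab is counted in none of the three windows. A programmer who works in elapsed days would get different responder counts from the same data. These variables feed both frequency tables and, where data suffice, logistic regression.

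**Working it through.** **Inputs**
- Interval length L = end − start + 1, and weeks = L / 7 (SAP 6.1.3).
- Windows: 1, 2 and 3 weeks for the Prevention populations and Part 1 Treatment; 8 and 29 days for Part 2 Treatment and Part 3 (SAP 6.16.1.3).
- Swabs every 7 days, plus or minus 2 days from Day 8 (Protocol 1.3.1).

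**Step 1: the windows that the SAP states in days.** For a Day 1 positive:
- Negative on Day 8: 8 − 1 + 1 = 8 days.
- Negative on Day 29: 29 − 1 + 1 = 29 days.

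Both match the stated 8- and 29-day windows exactly, so those windows fit the plus-1 count.

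**Step 2: the windows stated in weeks, visits on schedule.**

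| Days from positive to negative | L (days) | Weeks = L / 7 | Window limit | Inside? |
|---|---|---|---|---|
| 7 | 8 | 1.14 | 1 | No |
| 14 | 15 | 2.14 | 2 | No |
| 21 | 22 | 3.14 | 3 | No |

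The longest gaps that qualify are 6, 13 and 20 days. Without the plus 1, gaps of 7, 14 and 21 days give exactly 1, 2 and 3 weeks and qualify. A Day 1 positive with a Day 8 negative therefore meets the first milestone in Part 2 Treatment and Part 3 but fails it in Part 1 Treatment, on identical dates.

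**Step 3: visits spread over the visit window.** Let the positive swab be a days and the negative swab b days off schedule, each from −2 to +2. This gives 25 combinations, taken as equally likely. That is an assumption, because the documents give no visit-timing data. For the swab k weeks later the gap is 7k + b − a.
- Plus-1 rule: inside if 7k + b − a + 1 ≤ 7k, that is b − a ≤ −1. This holds in 10 of 25 (40%).
- Elapsed days: inside if b − a ≤ 0. This holds in 15 of 25 (60%).
- With the positive fixed on Day 1: 2 of 5 (40%) and 3 of 5 (60%). Under the plus-1 rule only Days 6–7, 13–14 and 20–21 qualify for the Day 8, 15 and 22 visits.

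With every visit on schedule the figures are 0% and 100%.

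**Step 4: how the documents use weeks elsewhere.** SAP 6.10.1 equates Day 57 with eight weeks after randomization. The four-week infection endpoint in SAP Table PYAD.4.1 is analysed by Day 29 in SAP 6.10.3.2. Elapsed time gives (57 − 1) / 7 = 8 and (29 − 1) / 7 = 4. The 6.1.3 formula gives 57 / 7 = 8.14 and 29 / 7 = 4.14. Two conventions are therefore in use.

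**The case against.** The strongest reply is that 6.1.3 was never meant to govern these windows. The primary endpoint, the four-week infection endpoint and the protocol's pairing of 24 weeks with Day 169 and 12 weeks with Day 85 all count elapsed weeks. On that usage, one, two and three weeks from baseline are Days 8, 15 and 22. SAP 6.1.3 also separates computing a length from deciding whether a date lies in an interval, reads its Day 29 and Day 57 limits as inclusive of the visit, and extends similar definitions to other endpoints. The explicit plus-1 formula in 6.16.1.4 belongs to a different endpoint.

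This shows that a programmer might not apply 6.1.3 literally. It does not exempt the clearance windows. The visit-inclusive wording concerns limits tied to a named visit, whereas clearance in the Prevention populations runs from each participant's own first positive. Elapsed days would also still miss 40% of the intended swabs under the even-spread assumption, so that reading does not settle the matter.

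The objection is right about the size of the effect. A reader might infer that the 1-week rate will be empty, or that only early attenders can ever count as cleared. Neither follows. A visit one or two days early can qualify. A participant negative at the first weekly swab counts within two and three weeks even if that swab was on time or late. Nor is the miss caused by missing-data imputation: the negative result is observed, and the participant simply fails the criterion, which SAP 6.3.3 classes as non-response.

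**Conclusion.** The point holds as a conflict between counting conventions that misplaces on-schedule clearances. Applied as written, SAP 6.1.3 puts swabs taken exactly 7, 14 and 21 days after the first positive at 1.14, 2.14 and 3.14 weeks, outside their own windows, so on-schedule clearances are reported one window late. This conflicts both with the SAP's elapsed-week usage and with the 8- and 29-day windows in the same section. The step 2 result needs only the SAP formula and the weekly schedule. The 40% and 60% figures also rest on the assumed even spread of visits.

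A reader might go further and infer a biased treatment comparison or a threat to the main results. The documents support neither. The rule and the swab schedule are the same in every arm of blinded Part 1 and of the Part 2 Prevention Cohort, and no directional effect is shown. The clearance proportions are exploratory and outside the multiplicity scheme of SAP 6.5. The primary and key secondary endpoints use Day 57 and Day 29 limits, so their results, alpha and sample size do not change.

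**What to change.** In SAP 6.16.1.3, define the three windows for the Prevention populations and Part 1 Treatment as clearance by the first, second and third planned weekly swab after the first positive, whatever the actual day within the visit window. State that the week conversion in 6.1.3 does not apply to them. This keeps all 25 of the 25 combinations in step 3.

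A day limit with the 2-day tolerance added is not equivalent. With limits of 9, 16 and 23 elapsed days, the condition is b − a ≤ 2, which 22 of 25 combinations (88%) meet.

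At a minimum, write the windows as 8, 15 and 22 days under the plus-1 count, in line with the 8 and 29 days already used for Part 2 Treatment and Part 3. That restores on-schedule swabs but not late ones (60% under the same assumption).

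The cost is one sentence in the SAP. No change to data collection or design is needed.
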